16.4 Publications

The preparation and submittal for publication of manuscripts containing the study results shall be in accordance with a process determined by mutual written agreement among the study Sponsor and participating institutions. The publication or presentation of any study results shall comply with all applicable privacy laws, including, but not limited to, the Health Insurance Portability and Accountability Act of 1996.

16.5 Investigator Responsibilities

By signing the Agreement of Investigator form, the Investigator agrees to:

1. Conduct the study in accordance with the protocol and only make changes after notifying the Sponsor (or designee), except when to protect the safety, rights or welfare of subjects.
2. Personally conduct or supervise the study (or investigation).
3. Ensure that the requirements relating to obtaining informed consent and IRB review and approval meet federal guidelines, as stated in § 21 CFR, parts 50 and 56.
4. Report to the Sponsor or designee any AEs that occur in the course of the study, in accordance with §21 CFR 312.64.
5. Ensure that all associates, colleagues and employees assisting in the conduct of the study are informed about their obligations in meeting the above commitments.
6. Maintain adequate and accurate records in accordance with §21 CFR 312.62 and to make those records available for inspection with the Sponsor (or designee).
7. Ensure that an IRB that complies with the requirements of §21 CFR part 56 will be responsible for initial and continuing review and approval of the clinical study.
8. Promptly report to the IRB and the Sponsor (or designee) all changes in the research activity and all unanticipated problems involving risks to subjects or others (to include amendments and IND safety reports).
9. Seek IRB approval before any changes are made in the research study, except when necessary to eliminate hazards to the patients/subjects.
10. Comply with all other requirements regarding the obligations of clinical investigators and all other pertinent requirements listed in § 21 CFR part 312.

Appendix 1: Schedule of Events

	Visit 1 - Screen up to 30 days before Visit 2	Document Initial Management Plan	Visit 2 - Day of ¹⁸ F-fluciclovine PET/CT				Visit 3	Document Post 18F-Fluciclovine PET/CT Management Plan	End of Study
			Pre-dose/pre-scan	Immed. post scan	60 min post dose	120 min post dose			
Study Day	-30 to Visit 2	Prior to Visit 2	1				2	2-22	180 ± 28 days
Visit Location/Type	Treating Physician Office	NA	PET/CT Imaging Center				Phone Call	NA	NA
Assessments/Procedures									
Informed consent	X								
Inclusion/ exclusion criteria	X		X						
Medical history	X		X						
PCa history, including treatment	X								
Record PSA levels ¹	X								X
Record imaging studies ²	X								X
Vital signs (heart rate and blood pressure)	X		X	X	X	X			
Height, weight			X						
Serum chemistry and hematology	X			X ³					
Serum PSA	X								
Urinalysis, dipstick	X ⁴								
EKG			X	X ³					
Record biopsy results, if applicable									X
Injection site assessment			X	X	X	X	X		
AE assessment				X	X	X	X		X
Concomitant medication assessment	X		X						X
Document management/plan		Plan						Revised	Actual
Treatment response assessment									X

1 - Record all available PSA levels obtained prior to Visit 1 through End of Study; for non-prostatectomy subjects, the PSA nadir and 2 times over nadir result must be documented in the record.

2 - Record all available imaging studies performed prior to Visit 1 through End of Study; negative or equivocal imaging within 60 days of Visit 1.

3 - Post-dose blood tests and EKG may be performed at the Imaging Center or within 7 days of the scan at another laboratory/site. *May be collected and tested at any time between screening and scan date

MRI	Magnetic Resonance Imaging
ms	Milliseconds
NPV	Negative Predictive Value
PCa	Prostate Cancer
PET	Positron Emission Tomography
PPS	Per Protocol Set
PPV	Positive Predictive Value
PSA	Prostate Specific Antigen
PT	Preferred Term
SAE	Serious Adverse Event
SAF	Safety Analysis Set
SAP	Statistical Analysis Plan
SD	Standard Deviation
SOC	System Organ Class
TEAE	Treatment Emergent Adverse Event
TN	True Negative
TNM	TNM Classification of Malignant Tumours
TP	True Positive
WHO	World Health Organization
WHO DDE	WHO Drug Dictionary Enhanced

1 INTRODUCTION

This Statistical Analysis Plan (SAP) is based on protocol version 3 dated 7th June 2017.

The SAP describes the tables, listings and figures which will be provided upon completion of the study. The SAP will be finalised before locking the database.

The table, listing and figure shells will be supplied in a separate document.

The analyses relating to the fifth secondary objective “To explore differences in estimated cost of treatment plans determined prior to and following ¹⁸F-fluciclovine PET/CT” will be reported separately and are not covered in this SAP.

2 GENERAL PRINCIPLES

The analysis and statistical reporting will be conducted at Syne qua non using SAS version 9.2 or higher.

All listings will be based on all enrolled subjects unless specified otherwise. All tables will be presented by site and overall for the appropriate analysis population.

Descriptive summary statistics for continuous variables will include number of subjects (n), mean, standard deviation (SD), minimum, median, and maximum, unless specified otherwise. The precision of these summary statistics is defined in the table, figure and listing shells document.

Descriptive summary statistics for categorical variables will include frequency counts and percentages [N (%)]. Unless stated otherwise, the denominator for percentage calculations will be the number of subjects in the analysis set.

There will be no imputation of missing data.

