Actual Management Plan. At the final follow up visit any deviations or changes to the Revised Management Plan will be documented

9. Biopsy

Biopsy is not required by the protocol; however patients with PET/CT positive findings in soft-tissue supported by anatomical abnormalities on CT or MRI may have a biopsy performed per standard practice where the procedure is deemed clinically feasible and safe. Biopsies completed within 4 months after imaging will contribute to the aim of the study.

1. Biopsy results of suspected bone metastases conducted per standard practice will also be collected. Bone lesions may be followed up through imaging where biopsy is not practical.
2. Based on local-radiologist/nuclear medicine physicians assessment of ¹⁸F-fluciclovine PET/CT-positive findings supported by anatomic abnormalities, conduct imaging-guided biopsy of soft-tissue ¹⁸F-fluciclovine -enhancement region per institutional standard of care;
3. Submit pathology report(s) to the ACR Core Laboratory. The address is given in the Imaging Manual.

10. Blood Chemistry Profile

Blood will be obtained and sent to each site's clinical chemistry lab for determination of serum sodium, potassium, calcium, chloride, BUN, creatinine, glutamic oxaloacetic transaminase (SGOT/AST), glutamic-pyruvic transaminase (SGPT/ALT), alkaline phosphatase, creatine kinase (CK), lactate dehydrogenase (LDH), albumin, total protein, total bilirubin.

11. Hematology

Blood will be obtained and sent to each site's clinical hematology lab for a complete blood count (hemoglobin, hematocrit, red blood cell count, white blood cell count, white blood cell differential, and platelet count determinations).

12. Urinalysis

Prior to the ¹⁸F-fluciclovine dosing a midstream sample of urine will be obtained and tested by dipstick for leukocytes, nitrite, pH, protein, ketones, glucose, bilirubin, urobilinogen, and blood. This will not be repeated following scanning unless clinically indicated.

13. Adverse Events

See Section 12.

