4 STUDY SUBJECTS

4.1 Analysis sets

The list of subjects to be included in each of the analysis sets is to be agreed between the Syne qua non statistician and Blue Earth Diagnostics once all study data are available and prior to database lock.

Enrolled Set: All subjects who entered screening.

Safety Analysis Set (SAF): All subjects who have been included in the database and have been administered ^{18}F -fluciclovine will be included in the Safety Analysis Set (SAF).

Full Analysis Set (FAS): All subjects enrolled who have had an ^{18}F -fluciclovine PET/CT scan will be included in the Full Analysis Set (FAS).

Evaluable Analysis Set (EAS): All subjects from the FAS who have an intended treatment management plan completed and a revised management plan page completed will be included in the Evaluable Analysis Set (EAS).

Per Protocol Set (PPS): All subjects in the EAS who meet the second and third protocol inclusion criteria (see protocol section 6.2) and any other subject without major significant deviation following review of the protocol deviation list.

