5.4.2 Secondary Efficacy Analyses

5.4.2.1 Change in actual management plan

The number, percentage and exact 95% CI for the percentage of subjects in the EAS with clinically significant deviations in actual management from the revised management plan after ¹⁸F-fluciclovine PET/CT scan results become available will be presented for overall and for subjects with positive and with negative ¹⁸F-fluciclovine PET/CT scans.

All management plan deviations will be listed in full.

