5.4.2.4 Treatment response as assessed by change in PSA

Baseline PSA is the most recent PSA measurement prior to salvage therapy for subjects who had salvage treatment and the most recent PSA measurement prior to the ^{18}F -fluciclovine PET/CT for non-salvage subjects. Treatment response, which is based on the percentage change in PSA from baseline to the last value reported, is defined as:

- $\geq 30\%$ decrease in PSA will be considered to be a response to treatment
- $<25\%$ increase or $<30\%$ decrease will be classified as stable disease
- $\geq 25\%$ increase in PSA will be classified as disease progression

The number, percentage and exact 95% CI of subjects having a treatment response, stable disease and disease progression, as assessed by change in PSA, will be presented overall and separately for subjects in the EAS who had salvage treatment, for subjects who had non-salvage treatment, for those with a change in management plan and for subjects with no change in management plan, by treatment and by disease location (Local disease/Extra-prostatic disease) following the ^{18}F -fluciclovine PET/CT scan.

In addition, the percentage change in PSA from baseline to the last value reported will be summarised overall and by subjects who had a change in management plan versus those who did not have a change in management plan following the ^{18}F -

fluciclovine PET/CT scan. The percentage change in PSA from baseline to the last value reported will also be summarised for subjects who had disease in the prostate only and for subjects who have extra-prostatic disease and by treatment.

Finally, a waterfall plot of the maximum percentage reduction in PSA during the 4-8 month window will be presented on the y-axis and each subject will be represented by a bar on the x-axis. The bars will be ordered in descending order of the magnitude of the percentage change in PSA value.

Treatment response and the factors used to assess the response will be listed in full.

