6 SAFETY EVALUATION

All safety evaluations will be performed on the safety analysis set (SAF) unless specified otherwise.

All safety tables will be presented by centre and overall.

Subjects will be included and counted in summary tables only if they have available data.

For laboratory parameters, vital signs and ECG, baseline will be defined as the last measure prior to fluciclovine (^{18}F) administration including day of administration if available.

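### In the actual-management analysis (SAP 5.4.2.1), an EAS subject with no End of Study record stays in the denominator and is in effect counted as having no deviation

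*SAP*

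**What the plan says.** SAP section 2 (General Principles) gives the rule for percentages: "Unless stated otherwise, the denominator for percentage calculations will be the number of subjects in the analysis set". The same section, and SAP 5.4.3, rule out imputing missing data.

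SAP 4.1 defines the EAS as those scanned subjects "who have an intended treatment management plan completed and a revised management plan page completed". Protocol 10.5 and Appendix 1 put the revised plan at days 2 to 22 after the scan, so EAS membership is settled within about three weeks.

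SAP 5.4.2.1 reports, with an exact 95% CI, the "percentage of subjects in the EAS with clinically significant deviations in actual management from the revised management plan". It names no other denominator, no completeness condition and no missing category. The source of the information is given in Protocol 9.2: "At the final follow up visit any deviations or changes to the Revised Management Plan will be documented". Protocol 10.6 times this at 26 ± 4 weeks.

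For PSA, SAP 5.4.2.4 asks for "The number, percentage and exact 95% CI of subjects having a treatment response, stable disease and disease progression". It classifies on the change from baseline to the last reported value and gives no rule for a subject with no value after baseline.

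The safety section does have an available-data rule: "Subjects will be included and counted in summary tables only if they have available data". The efficacy section has no equivalent.

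**The concern.** A subject can qualify for the EAS by day 22 and have no actual-management record five months later. Protocol 10.8 lists loss to follow-up and withdrawal among the reasons for discontinuation, and keeps a withdrawn subject's data in the analysis if the baseline measures are complete. Under the stated rules such a subject is divided by but cannot be counted as deviating.

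Two things follow. The deviation rate is pulled down by the proportion missing. The exact interval is computed as if the unobserved subjects had been observed, so it is too narrow for the information available.

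As SAP 5.4.2.1 is written, with the revised plan as comparator, the effect is to make adherence to the revised plan look better than the data show. The listed secondary endpoint compares actual management with the intended plan. That difference of comparator is a separate matter, but on that comparison the same dilution would understate the impact of the scan.

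**Working it through.** **The plan's own figures.** No six-month loss rate is stated, so there is no planned figure for this analysis to reproduce. The sample-size chain in Protocol 14.4, which supplies the 248 used below, does reproduce:

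- 89 / 0.40 = 222.5, rounded up to 223.
- P(at least 89 positive among 248, at 40%) = 0.918, which meets the 90% target.
- 248 / (1 − 0.15) = 291.8, rounded up to 292.

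**Formula.** Let N be the EAS size, m the number with no actual-management record, d = m/N, and x the number deviating among the N − m observed.

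- Available-data rate: x / (N − m)
- Rate under SAP 2 and 5.4.2.1: x / N = [x / (N − m)] × (1 − d)
- All missing counted as not deviating: x / N, identical to the reported rate
- All missing counted as deviating: (x + m) / N

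**Assumptions.** N = 248, d from 5% to 20%, and about 30% deviating among those observed. None of these is a documented value for this endpoint. Intervals are Clopper-Pearson 95%.

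| Missing (m) | Available data | Reported under the SAP rule | All missing deviate |
|---|---|---|---|
| 5% (12) | 71/236 = 30.1% (24.3–36.4) | 71/248 = 28.6% (23.1–34.7) | 83/248 = 33.5% |
| 10% (25) | 67/223 = 30.0% (24.1–36.5) | 67/248 = 27.0% (21.6–33.0) | 92/248 = 37.1% |
| 15% (37) | 63/211 = 29.9% (23.8–36.5) | 63/248 = 25.4% (20.1–31.3) | 100/248 = 40.3% |
| 20% (50) | 59/198 = 29.8% (23.5–36.7) | 59/248 = 23.8% (18.6–29.6) | 109/248 = 44.0% |

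Check at 15%: 29.9% × (1 − 37/248) = 29.9% × 0.851 = 25.4%. The interval is 31.3 − 20.1 = 11.2 points wide under the SAP rule, against 36.5 − 23.8 = 12.7 points on the observed subjects.

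The relative shrinkage depends only on d, not on the deviation rate. At 15% missing, 21/211 = 10.0% becomes 21/248 = 8.5%, and 106/211 = 50.2% becomes 106/248 = 42.7%.

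**PSA response.** A subject with any PSA after baseline is classified on the last one, whether or not it is a six-month value. A subject with none has no percentage change. He meets none of the three definitions but remains in the denominator, so response, stable disease and progression are all diluted and their percentages sum to less than 100%.

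**Primary endpoint.** The EAS definition requires both plans that the primary analysis compares, so the analysis set and the observed set coincide.

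**The case against.** The case on the other side has several parts.

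- *Loss need not mean a missing form.* Under Protocol 10.6 the treating physician completes the questionnaire and the remaining data are abstracted from the medical record. Appendix 1 lists no visit location for End of Study. A reader might infer that every subject who withdraws, is lost or dies drops out of the numerator. The documents do not support that, because treatment already given can still be recorded. The point applies only where the record is actually absent.
- *The 15% is not a six-month loss rate.* A reader might take it as the protocol's expectation for this endpoint. Protocol 14.4 uses it for the primary aim, to go from 248 to 292, so 248 is already net of it. Taking a further 15% off 248 and presenting it as planned loss would imply 1 − 211/292 = 27.7% lost overall, which the protocol does not say. Hence the range above, labelled as assumption.
- *PSA response.* A reader might infer that anyone without six-month data is counted as a non-responder. The last-value rule in SAP 5.4.2.4 contradicts that. Even a subject with no post-baseline value is left unclassified rather than assigned to non-response, unless the baseline itself were read as his last value, which would make him stable.
- *The available-data rate is not the truth either.* It is unbiased only if missingness is unrelated to deviation. This is correct, and it is why bounds are needed as well as a new denominator.
- *Partial cover elsewhere.* SAP 4.2 tabulates withdrawals with reasons, 5.4.2.1 lists all deviations, and the table shells are a separate document that may include a missing row. But withdrawal counts are not counts of missing actual-management records, and nothing in the SAP text requires such a row.

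These arguments limit the likely size and confine the PSA part. None of them removes the arithmetic consequence of combining SAP 2, 4.1 and 5.4.2.1.

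**Conclusion.** The point holds for actual management. Applied as written, the SAP reports the lower bound of the deviation rate as if it were the estimate, with an interval that treats unobserved subjects as observed. The relative understatement against the available-data rate equals the missing fraction. On the illustrative figures this is small at 5% missing (30.1% against 28.6%) and material at 15% (29.9% against 25.4%, with 40.3% as the opposite bound). The actual size depends on how many End of Study records are absent, which the documents do not indicate.

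For PSA response the gap is confined to subjects with no post-baseline value. The affected results are descriptive and secondary, with no test or decision rule attached, and the primary result is unaffected. The text should still be corrected before database lock, because it is a stated rule that works against the plan's own bar on imputation.

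**What to change.** In SAP 5.4.2.1, state that the denominator is the EAS subjects with a completed actual-management record. Beside each percentage, show the number of EAS subjects without one, by reason (withdrawn, lost, died, other). Add two bounding rates on the full EAS, one with all missing counted as changed and one with all counted as unchanged.

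In SAP 5.4.2.4, state that the denominator is subjects with a baseline and at least one post-baseline PSA, and show how many have none.

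The cost is SAP wording and a few extra table rows, with no new data collection. The downside is a slightly smaller n and slightly wider intervals, for example 12.7 rather than 11.2 points in the 15% illustration.

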3 STUDY OBJECTIVES AND DESIGN

3.1 Study Objectives

The primary objective of the study is to measure the fraction of subjects for whom ¹⁸F-fluciclovine PET/CT alters intended management through detection of disease after curative-intent treatment in a population of men with elevated prostatic specific antigen (PSA) levels indicative of persistent or recurrent prostate cancer and negative or equivocal findings on standard-of-care diagnostic imaging tests.

The secondary objectives of the study are

- To measure the fraction of subjects for whom ¹⁸F-fluciclovine PET/CT leads to a change in actual management by comparison with the intended management plan before ¹⁸F-fluciclovine PET/CT
- To estimate the fraction of subjects in whom ¹⁸F-fluciclovine PET/CT yields evidence of recurrent disease on the basis of imaging results
- To estimate:

- the rates of detecting regionally recurrent disease (i.e. prostatic bed-only and/or pelvic disease outside of the bed)
 - the rate of detecting distant metastases (i.e. bone metastases, visceral metastases, or non-regional nodal metastases)
- with ^{18}F -fluciclovine PET/CT in the study population
- To determine:
 - the positive predictive value (PPV) of ^{18}F -fluciclovine PET/CT to detect regionally recurrent disease
 - the PPV of ^{18}F -fluciclovine PET/CT to detect distant metastases in the study population in subjects who undergo optional biopsy of ^{18}F -fluciclovine PET/CT findings or have documentation of disease status based on other imaging and/or follow-up data
 - To explore differences in estimated cost of treatment plans determined prior to and following ^{18}F -fluciclovine PET/CT

[figure not shown]
3.2 Study Design

This is a phase IIIb open-labelled, multi-centred study to assess the impact on subject management of ^{18}F -fluciclovine PET/CT in subjects with rising prostate specific antigen (PSA) after initial cancer treatment.

The prospective study will enrol up to 330 men with PSA-recurrent prostate cancer after curative-intent primary therapy and negative or equivocal findings on standard-of-care imaging. Consenting participants will be imaged with ^{18}F -fluciclovine PET/CT. Site clinicians will manage study subjects per standard practices and will document any change in treatment based on review of the ^{18}F -fluciclovine PET/CT findings. Additionally, as clinically indicated, optional biopsy will be performed. All participants will be followed for up to 6 months, with clinical data collected for this study: PSA measurement from scan for 6 months. Treatment response will be assessed 6 months post scan.

The summary flowchart of the study design is as follows:

STUDY SCHEMA

3.3 Visit Structure

The visit structure and scheduled assessments are detailed in Appendix 1: Schedule of Events of the protocol.

3.4 Sample Size

The primary objective of this study is to measure the fraction of subjects for whom ¹⁸F-fluciclovine PET/CT alters the intended management plan. The sample size consideration is primarily based on the binding width of its 95% confidence interval, i.e. precision analysis. The prevalence of positive ¹⁸F-fluciclovine PET/CT findings in this population is assumed to be approximately 40%. About 30% of the positive scans are expected to change the physician's intended management plan. The goal is to accurately assess the fraction of change in intended management in these subjects. The table below lists the calculated sample sizes with respect to binding different 95% CI widths at the proportion of 30%. The Clopper-Pearson Exact method was used in PASS 12 (Hintze, 2013).

Confidence Level	Sample Size (N)	Target Width	Actual Width	Proportion (P)	Lower Limit	Upper Limit	Width If P=0.5
0.950	341	0.100	0.100	0.300	0.252	0.352	0.109
0.950	89	0.200	0.199	0.300	0.207	0.406	0.216
0.950	40	0.300	0.300	0.300	0.166	0.465	0.324

If the goal is to bind the 95% CI width at 0.20 then 89 FACBC positive subjects will be needed for the assessment of the primary aim. Since the positivity rate is assumed to be approximately 40% in the study population, 223 subjects need to be enrolled. After accounting for the random nature of the observed numbers of subjects meeting the clinical criteria in a prospective study and potential data loss, it is planned to enrol at least 292 and up to 330 subjects in order to obtain 89 evaluable subjects.

